8.1. OVERALL RESPONSE RATE (ORR)

ORR is defined as the proportion of subjects with objective evidence of complete response (CR) or partial response (PR) among the number of subjects evaluable for antitumor activity based on RECIST.

At the analysis stage, the best overall response (BOR) will be assigned for each subject as the best response recorded after initiation of study treatment, where the confirmation of CR or PR is required. The BOR assignment will follow the table below.

Table 3 – Best overall response when confirmation of CR and PR required.		
Overall response First time point	Overall response Subsequent time point	BEST overall response
CR	CR	CR
CR	PR	SD, PD or PR ^a
CR	SD	SD provided minimum criteria for SD duration met, otherwise, PD
CR	PD	SD provided minimum criteria for SD duration met, otherwise, PD
CR	NE	SD provided minimum criteria for SD duration met, otherwise NE
PR	CR	PR
PR	PR	PR
PR	SD	SD
PR	PD	SD provided minimum criteria for SD duration met, otherwise, PD
PR	NE	SD provided minimum criteria for SD duration met, otherwise NE
NE	NE	NE
CR = complete response, PR = partial response, SD = stable disease, PD = progressive disease, and NE = inevaluable.		

a If a CR is truly met at first time point, then any disease seen at a subsequent time point, even disease meeting PR criteria relative to baseline, makes the disease PD at that point (since disease must have reappeared after CR). Best response would depend on whether minimum duration for SD was met. However, sometimes 'CR' may be claimed when subsequent scans suggest small lesions were likely still present and in fact the patient had PR, not CR at the first time point. Under these circumstances, the original CR should be changed to PR and the best response is PR.

If applicable, responses recorded after initiation of new anticancer treatment will be excluded.

The BOR will be calculated separately for those subjects in the dose-escalation portion of the study (Part A), in the dose-expansion portion of the study (Part B), and in the combination therapy part of the study (Part C). The BOR will be summarized by cohorts for Part A, Part B, and Part C. In addition, the subjects who have SD more than 6 months will be summarized.

Summarization of ORR will be presented by frequency counts, percentage, and 95% CI. The CI will be obtained using an exact approach given the small sample size.

Syneos Health # 1006212

The sum of the diameters of all target lesions reported at each visit will be graphed by spider plot (% change in target lesion over time) and waterfall plot (best % change in target lesion). A swimmer plot will be used to display the characteristics of the overall responses over time.

In addition, listings of RECIST overall evaluation, target lesions, non-target lesions, and new lesion will be provided.

8.2. DISEASE CONTROL RATE (DCR)

DCR is defined as the proportion of subjects with objective evidence of CR, PR (where CR or PR requires confirmation), or SD (where the SD requires to occur at Cycle 4 or later).

The DCR will be calculated separately for those subjects in the dose-escalation portion of the study (Part A), in the dose-expansion portion of the study (Part B), and in the combination therapy part of the study (Part C).

Summarization of DCR will be presented by frequency counts, percentage, and 95% CI. The CI will be obtained using an exact approach given the small sample size.

8.3. DURATION OF RESPONSE (DOR) (PART B AND PART C)

DOR is defined as the time from the first documentation of response (CR or PR) to the first documentation of objective tumor progression or death due to any cause based on RECIST.

The DOR will be calculated for RECIST responders.

Censored subjects:

- Subjects who are alive and progression free as of the analysis cut-off date will be censored at their last evaluable tumor response assessment before initiation of any new anticancer treatment.
- Subjects with two or more consecutive missing response assessments prior to death or a visit with documented progression will be censored at the last date of tumor assessment when the subject was documented to be progression free.

Subjects who never achieve CR or PR prior to starting any new anti-cancer treatment at a lesion site will be excluded from the analysis.

If no CR/PR prior to starting any new anti- cancer treatment	excluded from the analysis
If responder (CR/PR) and then PD/death Without start of new anticancer	no censor

Version V3.0

Syneos Health # 1006212

If responder (CR/PR) and then start of new anticancer (with PD/death or not, after this start of new anticancer)	date of last evaluable tumor response assessment before new anticancer is censor date
If responder (CR/PR) and then PD/death	date of tumor assessment when the
Without start of new anticancer	subject was documented to be progression
But with two or more consecutive missing	free is censor date
response assessments prior to PD/death	

For Part B, the DOR will be calculated as follows (in weeks):

(date of PD /death in Part B - date of first response (CR or PR) in Part B + 1)/7

For Part C, the DOR will be calculated as follows (in weeks):

(date of PD/death in Part C - date of first response (CR or PR) in Part C + 1)/7

The distribution of DOR will be estimated for Part B and Part C using Kaplan-Meier methodology. The median point estimate DOR will be provided along with the two-sided 95% CIs for the antitumor evaluable population. Kaplan-Meier curves will be provided.

Part A DOR information will be listed only.

To help in interpretation of the response data, a table with change on the frequency of scans may be provided.

8.4. DURABLE RESPONSE RATE (PART B AND PART C)

Durable response rate is defined as the percentage of patients with an objective response (complete or partial response per RECIST1.1) lasting continuously for 6 months and starting any time within 12 months of initiating the study drug. The DRR will be summarized by each tumor type.

Summarization of DRR will be presented by frequency counts, percentage, and 95% CI. The CI will be obtained using an exact approach given the small sample size.

Analysis of Durable Response Rate will only be conducted as needed as the data allows.

8.5. PROGRESSION-FREE SURVIVAL (PFS) (PART B AND PART C COHORTS C5, C6, C7 ONLY)

PFS is defined as the time from the first dose of ALKS 4230 to the first documentation of objective tumor progression based on RECIST or death due to any cause.

The protocol stated that the PFS analysis will be only performed for Part B and Part C (Cohorts 5-7). The additional PFS analysis in ovarian patients from the PD-L1 unapproved

Syneos Health # 1006212

cohort will be conducted as ovarian is identified as one of tumor types to advance further clinical development in ALKS 4230 in combination with Pembrolizumab.

Subjects who do not have disease progression or have not died will be censored at the last known time that the subject was progression-free.

Censored subjects:

- If a subject begins a new anticancer treatment (either systemic or local) prior to documented progression or death, or a subject is removed from the study due to undocumented clinical disease progression, then the subject will be censored at the last assessment where the subject was documented as progression-free prior to the intervention.
- Subjects with two or more consecutive missing response assessments prior to a visit with documented progression (or death) will be censored at the last date of tumor assessment when the subject was documented to be progression free.

If no PD/death Without start of new anticancer	the last known time that the subject was progression-free is censor date
If start of new anticancer prior to PD/death or a subject is removed from the study due to undocumented clinical disease progression	date of last assessment where the subject was documented as progression-free prior to the intervention is censor date
If two or more consecutive missing response assessments prior to PD/death	date of the last date of tumor assessment when the subject was documented to be progression free is censor date

For Part B, the PFS will be calculated as follows (in weeks):

(date of PD /death in Part B - first dose date in Part B + 1)/7

For Part C, the PFS will be calculated as follows (in weeks):

(date of PD /death in Part C- first dose date in Part C + 1)/7

The survival distribution of PFS will be estimated using Kaplan-Meier methodology. The median RECIST PFS will be provided along with the two-sided 95% CIs based on the antitumor evaluable population. In addition, Kaplan-Meier curves will be provided. The 6-month and one-year PFS rate will be estimated using the Kaplan-Meier estimate.

8.6. TIME TO RESPONSE (TTR) (PART B AND PART C)

TTR is defined as the time from the date of first dose of study drug to the first documentation of response (CR or PR) based on the RECIST.

The TTR will be calculated for RECIST responders.

For Part B, the TTR will be calculated as follows (in weeks):

(date of first response (CR or PR) in Part B - date of first study drug in Part B + 1)/7

For Part C, the TTR will be calculated as follows (in weeks):

(date of first response (CR or PR) in Part C - date of first study drug) in Part C + 1)/7

The TTR will be summarized with descriptive statistics by cohorts for Part B and Part C.

Version V3.0

Syneos Health # 1006212

9. SAFETY ANALYSES

The population used for safety analyses will be the Safety Population. Safety will be assessed on the basis of AEs, clinical laboratory data, ECG parameters, physical examinations, and vital signs.

9.1. EXTENT OF EXPOSURE

The ALKS 4230 administration profile will be summarized by each part and cohort for the safety population with respect to duration of exposure, number of doses by cycle, cumulative doses received, number of cycles, average number of ALKS 4230 per cycle, relative dose intensity, duration of treatment and duration of study follow-up time. Number of patients who missed the dose will also be summarized by planned dosing day and by cycle. Data will also be summarized for subjects with any infusion interruptions and reason for interruption, and subjects with dose adjustments.

For rollover subjects from Part A or Part B, subjects will start with 3ug/kg as per protocol. However, some subjects might start with 6ug/kg as Part C C1D1 dosing. Therefore, the 6ug/kg should be used in relative dose intensity calculation in the denominator as planned dose.

In addition, the dose might be adjusted (either increase or decrease the dose) due to tolerability or other reasons after C1D1. In the relative dose intensity calculation, C1D1 dose is carried forward to the end of treatment as planned dose regardless dose changes during the treatment period.

Duration of exposure (days) = last dose date - first dose date + 1.

Treatment duration (days) = end of treatment (EOT) date - first dose date + 1, in which the last cycle end date will replace EOT date if the latter is missing.

In case of missing last cycle end date for rollover subjects in Part A or Part B, treatment duration (days) will be calculated as Part C cycle 1 day 1 date - Part B cycle 1 day 1 date + 1. If rollover subjects missing last cycle end date in Part C, take the last dose date in Part C + 16 days as the last cycle end date.

Relative dose intensity (%) = $100 \times [\text{total dose received } (ug/kg) / \text{total protocol planned dose } (ug/kg)].$

Duration of study (days) = end of study (EOS) date - first dose date + 1.

For those subjects with infusion interruptions, the reason for interruption will be summarized. If the subject has multiple interruptions caused by the same reason, the subject is only counted once per reason category.

Syneos Health # 1006212

Dose reductions and treatment discontinuations will be recorded on the eCRF, along with the AE/SAE or DLT that was associated with the change in dosing.

ALKS 4230 and pembrolizumab will be administered at a medical facility or study center by study staff; therefore, compliance is ensured. The treatment compliance will not be analyzed.

9.2. DOSE-LIMITING TOXICITIES

A DLT is defined by any of the following events possibly, probably, or definitely related to ALKS 4230 that are observed during the interval from C1D1 through C2D15:

- Grade 4 neutrophil count decreased (neutropenia) that has not recovered to Grade 2 (≥1,000 cells/mm3) within 15 days of the start of the cycle or requires an urgent intervention (e.g., use of hematopoietic colony-stimulating factors) or is associated with clinically significant infection. Dosing with ALKS 4230 in the current cycle will not be stopped due to neutropenia in the absence of urgent intervention or clinically significant infection
- Febrile neutropenia (ANC <1,000 cells/mm3 with temperature >38.3° C [101° F]) that persists for more than 48 hours or requires an urgent intervention (eg, use of hematopoietic colony-stimulating factors) or is associated with clinically significant infection
- Grade 4 thrombocytopenia that does not recover to Grade ≤2 within 15 days of the start of the treatment cycle
- Thrombocytopenia with a platelet count <30,000 with clinically significant bleeding
- Any Grade 3 cardiac or central nervous system toxicity
- Liver transaminase elevation higher than 8 × ULN or total bilirubin higher than 6 × ULN that does not recover to Grade ≤2 or baseline within 1 week
- Grade 4 hypoalbuminemia
- Fever >40°C sustained for >24 hours
- Hypotension requiring the use of pressors (eg, phenylephrine or dopamine, administered for the purpose of increasing blood pressure) or prolonged hospitalization (>48 hours) for hypotension requiring medical intervention
- Grade 3 or higher electrolyte abnormalities that do not recover to Grade ≤1 within 48 hours following medical management

- Increase in amylase or lipase that meets 1 of the following criteria:
 - Asymptomatic Grade 4 elevation
 - Asymptomatic Grade 3 elevation that does not resolve within 14 days
 - $\circ~>3\times$ ULN with acute severe abdominal pain (other mild symptoms at Grade 3 will not be considered as DLTs)
- Grade 3 or higher nausea, vomiting, or diarrhea lasting longer than 48 hours despite maximum supportive care is a DLT.
- Any other Grade 4 non-hematologic toxicity or any other Grade 3 non-hematologic toxicity that does not resolve to Grade ≤2 within 96 hours, other than fatigue or anorexia. Fatigue and anorexia will not be considered DLTs.
- Any other toxicity or AE not defined above that results in subject removal from the study or discontinuation of dosing by the Investigator (dose delays during Cycle 2 or later are not considered DLTs)

Any laboratory value that meets the DLT criteria as described above must be confirmed with a second laboratory test for DLT criteria to be met.

Subjects without a DLT who receive fewer than 10 doses through C2D15 will be replaced at the same dose level if the minimum number of evaluable subjects has not been reached for the cohort. However, the subject may remain in the study if the Investigator feels the risk/benefit ratio is acceptable.

All DLTs will be summarized by system organ class and preferred term, and by cohort for Part A, and a corresponding listing of DLTs-like will be provided for Part A.

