## **14.3.** Study Populations

#### 14.3.1. Safety Population

In Part A and Part B, the safety population will include all subjects who received ALKS 4230. In Part C, all subjects exposed to ALKS 4230 or pembrolizumab will be included in the safety population. This population will be used for all safety analyses.

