4.5. SAFETY ENDPOINTS

Safety will be assessed using the following:

- DLTs
- Treatment-emergent adverse events (TEAEs)
- Laboratory Evaluations (hematology, coagulation, chemistry, urinalysis tests)
- Vital Signs (systolic and diastolic blood pressure, pulse, respiratory rate, and oral body temperature)
- ECG parameters (overall assessment; heart rate; RR, PR, QRS, and QTc intervals)
- ECOG Performance Status

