5. ANALYSIS SETS

5.1. SAFETY POPULATION

In Part A and Part B, the Safety Population will include all subjects who receive at least 1 dose of ALKS 4230. In Part C, the Safety Population will include all subjects who receive at least 1 dose of ALKS 4230 or pembrolizumab. The Safety Population will be used for all safety analyses.

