9.3. ADVERSE EVENTS

Adverse events will be analyzed in terms of TEAEs, which are defined as AEs that are newly occurring or worsening from the time of the first dose of study drug. Reported AE terms will be coded using MedDRA version 25.0 or higher. The severity of the toxicities of AEs will be graded according to the NCI CTCAE version 4.03 or higher.

The severity of toxicities of AE is graded as mild (grade 1), moderate (grade 2), severe (grade 3), life-threatening (grade 4), or fatal (grade 5).

The relationship to study treatment is evaluated as definitely related, probably related, possibly related, probably not related, and definitely not related. Events will be classified as related vs non-related. A related AE is an event with a relationship to treatment as definitely related, probably related, or possibly related to study drug; a non-related AE is an event with relationship to treatment as probably not related, or definitely not

Version V3.0

Syneos Health # 1006212

related. If the relationship to the study treatment is missing, the TEAE will be considered to be treatment-related for table summary purposes.

TEAEs will be summarized by SOC and PT and by cohort. Some outputs with TEAEs based on tumor type may be produced for submission purpose. TEAEs with onset after the last dose of the study treatment period are attributed to the treatment received during the treatment period. Both event and subject counts will be summarized. Subject counts will be complemented by percentages calculated using the number of subjects exposed to study drug as the denominator.

The following summaries will be provided:

- An overall summary of the number and percentage of subjects reporting TEAEs, serious TEAEs, grade 3 or higher AEs, death, treatment-related TEAEs, and TEAEs leading to study discontinuation, leading to treatment discontinuation, leading to dose reduction, leading to dose interruption
- TEAEs by SOC and PT (including all severity grades)
- Most common (>= 10%) TEAEs by SOC and PT
- TEAEs by SOC, PT, and worst severity grade
- TEAEs by SOC, PT, and highest relationship (Related, Not Related), for Part C the highest relationship to ALKS and Pembrolizumab will be summarized in separate tables
- ALKS 4230-related TEAEs by SOC and PT
- Pembrolizumab-related TEAEs by SOC and PT
- Serious TEAEs by SOC and PT
- Treatment-related Serious TEAEs by SOC and PT
- Grade 3 or higher related TEAEs by SOC and PT

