- TEAE leading to treatment discontinuation by SOC and PT
- TEAE leading to dose reduction by SOC and PT
- TEAE leading to dose interruption by SOC and PT
- Treatment-related TEAE leading to dose interruption
- TEAEs leading to study discontinuation by SOC and PT

Syneos Health # 1006212

- Related TEAEs leading to study discontinuation by SOC and PT
- TEAEs meeting DLT leading to study discontinuation by SOC and PT

The tables will be sorted by overall SOC alphabetically and then, within a SOC, by overall descending frequency of PT based on the subject count for the overall column.

5 PTs including Neutrophil count decreased, Haemoglobin decreased, Platelet count decreased, Supraventricular tachycardia, and Lymphocyte count decreased will be grouped into new PTs as Neutropenia, Anaemia, Thrombocytopenia, Supraventricular extrasystoles, and Lymphopenia respectively. The new grouped SOCs will be Cardiac disorders for the original PT of Supraventricular tachycardia, and Blood and lymphatic system disorders for the rest of 4 original PTs.

For summaries by SOC, PT, and intensity, subject is counted only once at the highest grade for which the event occurred in the SOC and the highest grade for each unique PT within that SOC.

In addition, AEs reported post 30 days of safety follow-up period may be summarized by SOC and PT and/or listed separately.

The original date and time will be shown on all listings of AEs. Listings will be provided for all TEAEs, AEs resulting in death, serious TEAEs, AESIs, DLTs and AEs leading to dose reduction, dose interruption and discontinuation.

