- Tabular display of data for concomitant medications should be presented by ATC4 Code with the highest occurrence in the Overall group in decreasing order, assuming all terms are coded. Within the ATC4 drug class, concomitant medications should be displayed in decreasing order of Preferred Term. If medications for more than 1 term are identical, they should then be sorted alphabetically.
- Tabular display of data for medical history should be presented by the medical history category with the highest occurrence in the Overall group in decreasing order. If incidence for more than 1 term is identical, they should then be sorted alphabetically.
- Missing descriptive statistics or p-values which cannot be estimated should be reported as "-".

Syneos Health # 1006212

- The percentage of subjects is normally calculated as a proportion of the number of subjects assessed in the relevant cohort (or overall) for the analysis set presented. However, careful consideration is required in many instances due to the complicated nature of selecting the denominator, usually the appropriate number of subjects exposed. Describe details of this in footnotes or programming notes.
- For categorical summaries (number and percentage of subjects) where a subject can be included in more than one category, describe in a footnote or programming note if the subject should be included in the summary statistics for all relevant categories or just 1 category and the criteria for selecting the criteria.
- Where a category with a subheading (such as system organ class) has to be split over more than one page, output the subheading followed by "(cont)" at the top of each subsequent page. The overall summary statistics for the subheading should only be output on the first relevant page.

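### Part A DLT incidence has no stated denominator, so the SAP's defaults count subjects not evaluable for DLT as DLT-free (minor reporting fix)

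*SAP*

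**What the plan says.** Protocol 6.4 and SAP 4.1 make the incidence of DLTs over the DLT observation period a Part A primary endpoint. The planned output is one sentence in SAP 9.2: "All DLTs will be summarized by system organ class and preferred term, and by cohort for Part A". It names neither a population nor a denominator.

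Four other places in the SAP supply defaults:

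- SAP 4.5, under "Safety will be assessed using the following", puts DLTs first in the list of safety endpoints.
- SAP 5.1 states: "The Safety Population will be used for all safety analyses". SAP 9, the parent section of 9.2, repeats it: "The population used for safety analyses will be the Safety Population". Protocol 14.3.1 agrees: "This population will be used for all safety analyses". In Part A this population is every subject given ALKS 4230.
- SAP 9.3 has adverse-event "percentages calculated using the number of subjects exposed to study drug as the denominator". Its list of tables includes one on DLTs: "TEAEs meeting DLT leading to study discontinuation by SOC and PT".
- SAP 13.2.5.2 asks for care in choosing denominators, "due to the complicated nature of selecting the denominator, usually the appropriate number of subjects exposed".

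Protocol 7.5 sets the evaluability rule: in dose escalation, a subject with no DLT and under 10 doses by Cycle 2 Day 15 is not evaluable for DLT, and is replaced if the cohort is short of its minimum. It also keeps replaced subjects' data in the analysis. Protocol 8.1 defines the MTD on evaluable subjects and allows cohorts of 4 to 7 with as few as 3 evaluable. SAP section 5 defines Safety, Antitumor Evaluable and Pharmacodynamic populations, but no DLT-evaluable set.

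**The concern.** The protocol holds that a subject who stopped short of the required doses without a DLT cannot inform the DLT question. The SAP's defaults put that subject in the denominator as a non-event. Each such subject lowers the reported incidence, and it can never rise, because a subject with a DLT is evaluable however few doses were given.

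What is at stake is the reporting of a primary endpoint. A reader comparing the DLT table with the escalation decisions could find a rate that does not match the one behind the decision. The response endpoint has its own evaluable set in SAP 5.2; the Part A primary endpoint has none.

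**Working it through.** The documents state no DLT rate, so there is no planned figure to reproduce. The check sets the rules side by side and then computes the gap for cohort sizes that the plan allows.

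**Inputs**

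- Evaluable: had a DLT, or received at least 10 doses by Cycle 2 Day 15 (Protocol 7.5). On the standard schedule this is 5 doses × 2 cycles = 10.
- Cohort size: 4 to 7 with over-enrolment, at least 3 evaluable (Protocol 8.1).
- Stopping: 2 or more subjects with a DLT at a dose level (Protocol 8.1).
- Evaluable and treated counts per cohort: not given, so the cases below are illustrations.

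**Formula.** With x DLTs, e evaluable subjects and k treated but unevaluable subjects, the evaluable rate is x/e and the treated rate is x/(e + k). The gap is

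x/e − x/(e + k) = xk / [e(e + k)].

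It is zero when k = 0 or x = 0, and never negative.

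**Results** (k = 1; exact Clopper-Pearson 95% intervals)

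| Case | Evaluable rate | Treated rate | Gap |
|---|---|---|---|
| 1 DLT, e = 6 | 1/6 = 16.7% (0.4 to 64.1) | 1/7 = 14.3% (0.4 to 57.9) | 1/42 = 2.4 points |
| 2 DLTs, e = 6 | 2/6 = 33.3% (4.3 to 77.7) | 2/7 = 28.6% (3.7 to 71.0) | 2/42 = 4.8 points |
| 2 DLTs, e = 3 | 2/3 = 66.7% (9.4 to 99.2) | 2/4 = 50.0% (6.8 to 93.2) | 2/12 = 16.7 points |

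**Neither denominator is free of bias.** Let p be the true DLT rate and u an assumed share of subjects who would stop short of the doses.

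- If those subjects stop before being at risk, the treated rate is p(1 − u).
- If they stop after the risk has passed, the evaluable rate is p / [p + (1 − p)(1 − u)], because the set keeps every DLT and loses only DLT-free subjects.

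For p = 1/3, these two extremes are:

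| Assumed u | Treated rate, at its lowest | Evaluable rate, at its highest |
|---|---|---|
| 5% | 31.7% | 34.5% |
| 1/7 | 28.6% | 36.8% |
| 25% | 25.0% | 40.0% |

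The documents give no value for u, so these rows show direction and scale only.

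**The case against.** **The SAP does not order a treated-subject denominator.** SAP 13.2.5.2 also bases percentages on subjects in the analysis set who have an observation, or who were assessed. A subject short of doses might be held not to have been assessed for DLT. The explicit exposed-subject rule sits in 9.3 and is written for adverse-event tables, and the table shells are in a separate document (SAP 15). This stands in part: the treated denominator is an inference. But both of those conventions start from the analysis set being presented, and SAP 5.1 and 9 name that set as the Safety Population.

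**The denominator would be partly visible.** Tables carry the analysis set under the title (SAP 13.2.3) and N per cohort (13.2.4). Doses by cycle and missed doses are summarised (9.1), DLTs are listed (9.2), and Protocol 14.2 promises listings of subject-level data. A determined reader could probably rebuild the evaluable count. This lowers the severity, but a primary endpoint should not need rebuilding.

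**The treated rate is defensible.** The endpoint runs from first dose, and Protocol 7.5 keeps replaced subjects in the analysis. This stands as a reason to report the treated rate as well. It does not justify reporting that rate alone.

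**Few subjects may be unevaluable.** Related toxicity within the window that leads the investigator to stop dosing is itself a DLT, and an over-enrolled seventh subject may be fully evaluable. Both points are right, and the gap may be zero. The first also means that leaving out unevaluable subjects should hide little toxicity.

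**A stronger reading.** A reader might infer that the SAP weakened the MTD definition, since SAP 3.4 omits the word *evaluable* that Protocol 8.1 uses. The documents do not support this: the protocol's own synopsis omits it too, so the inconsistency starts inside the protocol and changes no output.

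**Conclusion.** The point holds as a minor reporting gap. The SAP leaves the denominator of a Part A primary endpoint unstated, and its defaults most naturally give a rate diluted by subjects whom the protocol calls unevaluable. One such subject costs 2.4 to 4.8 points in a cohort with six evaluable subjects, and 16.7 points where two DLTs occur among three. These gaps are small against intervals as wide as 4.3 to 77.7%.

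Two larger conclusions are tempting and unsupported. The first is that the dose selection is in doubt: escalation was to be decided at Safety Review Committee review, and SAP 3.4 records the RP2D as already set at 6 µg/kg. The second is that a reported 2/7 would contradict the MTD by falling under one-third. Escalation stops on a count of DLTs, so 2/7 overturns nothing.

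The verdict assumes that the unseen table shells do not already specify an evaluable denominator and that at least one treated subject in a cohort with a DLT was unevaluable. If the second assumption fails, the two rates coincide.

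**What to change.** - In SAP section 5, add a DLT-evaluable set: Part A subjects who had a DLT from Cycle 1 Day 1 through Cycle 2 Day 15, or who by then had received at least 10 doses, or all planned doses on an alternative schedule. The last clause is needed because Protocol 8.1 permits fewer than 5 dosing days per cycle, and a fixed 10-dose threshold would then be out of reach.
- In SAP 9.2, use this set as the main denominator for DLT incidence by dose cohort, with the Safety Population rate in the next column.
- List the unevaluable subjects with doses received and reason for stopping.
- Optionally, align the MTD wording in the protocol synopsis and SAP 3.4 with Protocol 8.1.

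The cost is one analysis set, one table column and one listing, from dosing and disposition data already collected. No visit or dose decision changes. The downside is that the evaluable rate can run slightly high, which is why the two rates should appear together.
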